Participants experiencing a DLT will enter the safety follow-up period of the study. DLTs occurring after the 4-week DLT observation period for the Preliminary Safety Cohorts or 5-week DLT observation period for Parts A, B and C will be accounted for in determining the MAD for the combination part.

AEs will be graded according to the NCI CTCAE v4.03²⁷, as listed below:

A. Hepatic Non-hematological DLT

Any one of the following study treatment-related events will be considered a hepatic DLT:

- Any Grade \geq 3 elevation of AST, ALT, or total bilirubin.
- Grade 2 AST or ALT with symptomatic liver inflammation (eg, right upper quadrant tenderness, jaundice, pruritus).
- AST or ALT > 3× ULN and concurrent total bilirubin > 2× ULN without initial findings of cholestasis (elevated serum alkaline phosphatase [ALP] [eg, findings consistent with Hy's law or FDA definition of potential drug-induced liver injury or potential drug-induced liver injury [p-DILI]). Note that this special category of DLT uses ULN rather than Common Toxicity Criteria (CTC) grade for definition.

B. Non-hepatic Non-hematological DLT

Any of the following events will be considered a non-hepatic non-hematological DLT:

- Any Grade 2 drug-related uveitis or eye pain or blurred vision that does not respond to topical therapy and does not improve to Grade 1 severity ≤ 2 weeks *or* requires systemic treatment.
- Grade 3 drug-related uveitis, pneumonitis, bronchospasm, myocarditis, neurologic toxicity, hypersensitivity reaction, or infusion reaction of any duration will require discontinuation.
- Any Grade 3 or greater nondermatologic, nonhepatic nonhematological study treatment-related toxicity will be considered a DLT, with the following specific exceptions:
 - Grade 3 or Grade 4 electrolyte abnormalities that are not complicated by associated clinical adverse experiences, last \leq 72 hours, and either resolve spontaneously or respond to conventional medical intervention
 - Grade 3 nausea, vomiting, or diarrhea that lasts less than 72 hours (without steroid therapy) and either resolves spontaneously or responds to conventional medical intervention
 - Isolated Grade 3 elevation of amylase or lipase not associated with clinical or radiographic evidence of pancreatitis

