 - Isolated Grade 3 fever not associated with hemodynamic compromise (eg, hypotension, clinical or laboratory evidence of impaired end-organ perfusion or with other symptoms of infusion-related reactions that returns to ≤ Grade 1 with standard treatment in ≤ 1 hour

Revised Protocol No.: 04 Date: 31-May-2019

- Grade 3 endocrinopathy that is well controlled by hormone replacement
- Grade 3 tumor flare (defined as pain, irritation, or rash that localizes to sites of known or suspected tumor)
- Grade 3 fatigue for \leq 7 days
- Grade 3 infusion reaction that returns to Grade 1 in \leq 1 hour

C. Dermatologic DLT

- Grade 3/4 rash if no improvement (ie, resolution to Grade ≤ 1) after a 1-week to 2-week infusion delay. Participants who have not experienced a Grade 3 drug-related skin AE may resume treatment in the presence of Grade 2 skin toxicity.
- Grade 4 rash of any duration

D. Hematologic DLT

- Grade 4 neutropenia \geq 5 days in duration
- Grade 4 thrombocytopenia or Grade 3 thrombocytopenia with clinically significant bleeding or any requirement for platelet transfusion
- Grade 4 anemia not explained by underlying disease
- Grade 4 febrile neutropenia
- Grade 3 febrile neutropenia that lasts > 48 hours
- Grade \geq 3 hemolysis (i.e., requiring transfusion or medical intervention such as steroids)

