7.3.5 Exceptions to Permanent Discontinuation Criteria

Any drug-related AE occurring at any time that meets DLT criteria as outlined in Section 7.3.2 will require permanent discontinuation. Exceptions to permanent discontinuation are listed in Section 8.1.

Study treatment may be re-initiated in participants experiencing non-life-threatening AEs that meet DLT criteria and that have been resolved to Grade 1 or baseline. Consideration to resume treatment will be made on a case-by-case basis in a discussion between the investigator and BMS Medical Monitor/Study Director (or designee) and approval of the sponsor, taking into account the overall benefit/risk ratio for the individual participant and the following factors:

- A 2-week washout period is required after completing the immune suppressive treatment used to manage the AE (eg, steroids). The AE should not recur/worsen during the washout period.
- Evidence for clinical or radiographic benefit must be present, which can include improvement of physical symptoms (eg, ECOG status, shortness of breath), symptomatic improvement in combination with assessment of SD, or radiographic response.

In the event of recurrence of the AE that met the DLT criteria, study treatment will be permanently discontinued for the participant.

Additionally, consideration to permanently discontinue study treatment for participants with any severe Grade 3 drug-related AE that recurs will be made on a case-by-case basis in a discussion between the investigator and BMS Medical Monitor/Study Director (or designee).

All participants who discontinue IP should comply with protocol-specified follow-up procedures as outlined in Section 5.1.3. The only exception to this requirement is when a participant withdraws consent for all study procedures including post-treatment study follow-up or loses the ability to consent freely (eg, imprisonment or involuntarily incarceration for the treatment of either a psychiatric or physical illness).

If study treatment is discontinued prior to the participant's completion of the study, the reason for the discontinuation must be documented in the participant's medical records and entered on the appropriate Case Report Form (CRF) page.

7.3.6 *Management of Drug-related Infusion Reactions*

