BMS-986226 is a humanized mAb and has the potential to induce hypersensitivity reactions following administration. As of 28-March-2019, 7 of 19 (36.8%) participants treated with BMS-986226 monotherapy experienced a Grade 1 or Grade 2 infusion-related reaction. One participant experienced Grade 3 hypersensitivity during BMS-986226 infusion after the data cut-off date of 28 March 2019. When such reactions occur, they may manifest with fever, chills, rigors, headache, flushing, rash, urticaria, pruritus, arthralgia, hypotension, hypertension, bronchospasm, or other allergic-like reactions. All Grade 3 or 4 infusion reactions should be reported within 24 hours to the BMS Medical Monitor/Study Director (or designee) and reported as an SAE. Infusion reactions should be graded according to NCI CTCAE v4.03²⁷ guidelines.

Premedications are recommended as per section 7.1.

Treatment recommendations for infusion reactions are provided below and may be modified based on local treatment standards and guidelines, as appropriate.

For Grade 1 symptoms: Mild reaction; infusion interruption not indicated; intervention not indicated.

• Remain at bedside and monitor participant until recovery from symptoms. The following prophylactic premedications are recommended for future infusions: diphenhydramine 50 mg (or equivalent) and acetaminophen/paracetamol 325 to 1,000 mg at least 30 minutes before study treatment administrations.

For Grade 2 symptoms: Moderate reaction requiring therapy or infusion interruption but responding promptly to symptomatic treatment (eg, antihistamines, nonsteroidal-anti-inflammatory drugs, narcotics, corticosteroids, bronchodilators, or IV fluids); prophylactic medications indicated for ≤ 24 hours.

- Remain at the bedside and monitor participant until resolution of symptoms. Monitor participant closely.
- Stop the study treatment infusion, begin an IV infusion of normal saline, and treat the participant with diphenhydramine 50 mg IV (or equivalent) and acetaminophen/paracetamol 325 to 1,000 mg.
- Corticosteroid and/or bronchodilator therapy may also be administered as appropriate.
- If the infusion is interrupted, then restart the infusion at 50% of the original infusion rate when symptoms resolve; if no further complications ensue after 30 minutes, the rate may be increased to 100% of the original infusion rate. The amount of study treatment infused must be recorded on the CRF.

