- If symptoms recur, then no further BMS-986226, nivolumab, or ipilimumab will be administered at that visit.
- For future infusions, the following prophylactic premedications are recommended: diphenhydramine 50 mg (or equivalent) and acetaminophen/paracetamol 325 to 1,000 mg should be administered at least 30 minutes before study treatment infusions. If necessary, corticosteroids (up to 25 mg of hydrocortisone or equivalent) may be used.

For Grade 3 or 4 symptoms: Severe reaction, Grade 3: prolonged (eg, not rapidly responsive to symptomatic medication and/or brief interruption of infusion); recurrence of symptoms following initial improvement; hospitalization indicated for other clinical sequelae (eg, renal impairment or pulmonary infiltrates); Grade 4: life-threatening; pressor or ventilatory support indicated.

- Remain at bedside and monitor participant until recovery of the symptoms.
- Immediately discontinue infusion of study treatment.
- Begin an IV infusion of normal saline and treat the participant as follows: recommend bronchodilators, epinephrine 0.2 to 1 mg of a 1:1,000 solution for intramuscular or subcutaneous administration or 0.1 to 0.25 mg of a 1:10,000 solution injected slowly for IV administration, and/or diphenhydramine 50 mg IV with methylprednisolone 100 mg IV (or equivalent), as needed.
- Participant should be monitored until the investigator is comfortable that the symptoms will not recur. Study treatment will be permanently discontinued except for a Grade 3 infusion reaction that returns to Grade 1 in less than 6 hours. Investigators should follow their institutional guidelines for the treatment of anaphylaxis.

In case of late-occurring hypersensitivity symptoms (eg, appearance of a localized or generalized pruritus within 1 week after treatment), symptomatic treatment may be given (eg, oral antihistamine or corticosteroids).

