8.1.1 Criteria to Resume Treatment

Subsequent dosing with the study treatment may resume once drug-related DLT AEs resolve to Grade 1 or baseline.

In agreement with the Sponsor, after evaluation of the risk/benefit ratio, participants with selected drug-related AE that meet DLT criteria may resume treatment once the AE is resolved to Grade ≤ 1 or baseline value (see Section 7.3.5).

Participants who experience AEs and do not meet the criteria for permanent discontinuation as outlined in Section 8.1 may resume study treatment under the following criteria:

- Participants may resume treatment with study treatment when the drug-related AE(s) resolve to Grade ≤ 1 or baseline value, with the following exceptions:
 - Participants may resume treatment in the presence of Grade 2 fatigue.
 - Participants who have not experienced a Grade 3 drug-related skin AE may resume treatment in the presence of Grade 2 skin toxicity.
 - Participants with Grade 2 uveitis, episcleritis, iritis, eye pain, or blurred vision not meeting DLT criteria (Section 7.3.2) must resolve to baseline prior to resuming study treatment.
- For participants with Grade 2 AST, ALT, or total bilirubin elevations, dosing may resume when laboratory values return to baseline and management with corticosteroids (if needed) is complete.
 - Participants with combined Grade 2 AST/ALT and total bilirubin values meeting DLT criteria (Section 7.3.2) should have treatment permanently discontinued.
- Drug-related pulmonary toxicity, diarrhea, or colitis must have resolved to baseline before treatment is resumed. Participants with persistent Grade 1 pneumonitis after completion of a steroid taper over at least 1 month may be eligible for retreatment if discussed with, and approved by, the BMS Medical Monitor/Study Director (or designee).
- Participants with drug-related endocrinopathies adequately controlled with only physiologic hormone replacement may resume treatment.

If the criteria to resume treatment are met, the participant should restart treatment at the next nominally scheduled time point per protocol.

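### Section 7.3.2 B makes a Grade 3 infusion reaction that settles within 1 hour both a DLT and not a DLT; between 1 and 6 hours only the stopping rules disagree

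*Combined protocol and SAP*

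**What the plan says.** Section 7.3.2 B opens with "Any of the following events will be considered a non-hepatic non-hematological DLT". Three bullets follow.

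- The second bullet reads "Grade 3 drug-related uveitis, pneumonitis, bronchospasm, myocarditis, neurologic toxicity, hypersensitivity reaction, or infusion reaction of any duration will require discontinuation".
- The third makes other treatment-related toxicities of Grade 3 or higher DLTs, subject to named exceptions. One exception is a "Grade 3 infusion reaction that returns to Grade 1 in" 1 hour or less.

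Other sections give rules on stopping:

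- Section 7.3.5: "Any drug-related AE occurring at any time that meets DLT criteria as outlined in Section 7.3.2 will require permanent discontinuation". It then allows case-by-case restart after a non-life-threatening DLT, with sponsor approval, a 2-week washout after immune suppression and evidence of benefit.
- Section 7.3.6: "Study treatment will be permanently discontinued except for a Grade 3 infusion reaction that returns to Grade 1 in less than 6 hours". The recommendations there carry the caveat "Treatment recommendations for infusion reactions are provided below and may be modified based on local treatment standards and guidelines, as appropriate".
- Section 8.1.1: "Subsequent dosing with the study treatment may resume once drug-related DLT AEs resolve to Grade 1 or baseline".
- Section 5.1.2.3, on DLTs in Parts B and C, calls for a temporary hold.

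**The concern.** The lead-in of 7.3.2 B makes every listed event a DLT, and the words on duration in the second bullet rule out a time limit. The third bullet then grants one to the same event. A site, or the sponsor and investigators at a dose meeting, could code a Grade 3 infusion reaction of up to 1 hour either way and cite the protocol for it.

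DLT counts feed the BLRM and BLRM-Copula, and adverse events meeting DLT criteria are part of the primary endpoint. Infusion reactions are also the most visible signal so far: 7 of 19 monotherapy participants had one of Grade 1 or 2 (Section 7.3.6).

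For reactions of 1 to 6 hours the DLT count is safe. What can vary is whether the participant stops treatment, which affects participant management and another primary component, adverse events leading to discontinuation.

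**Working it through.** **The rules side by side, by time to return to Grade 1**

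| Time | 7.3.2 B, second bullet | 7.3.2 B, third bullet | Stopping rules |
|---|---|---|---|
| up to 1 h | DLT | not a DLT | second bullet: discontinue; 7.3.6: exempt from permanent discontinuation |
| over 1 h, under 6 h | DLT | DLT | second bullet and 7.3.5: discontinue, conditional restart; 8.1.1: may resume at Grade 1 or baseline; 5.1.2.3: hold (Parts B and C); 7.3.6: exempt |
| 6 h or more | DLT | DLT | 7.3.6 also requires permanent discontinuation |

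Only the first row is a conflict about DLT status. Appendix 12 lists the 1-hour item among the DLT criteria edited or added in Revised Protocol 01. That suggests the exception was intended and the second bullet was not brought into line.

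**What one disputed event does to the model**

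Inputs from Appendix 10:

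- Model: logit(p) = log(α) + β·log(d/800).
- Prior: log(α) and log(β) normal with means −0.847 and 0, SDs 1.53 and 1, correlation 0.
- A dose is admissible if P(DLT rate ≥ 33%) is below 0.30.

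The posterior was obtained by grid integration (801 × 801 points, ±6 SD).

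Check against the plan's own example (0/3 at 25 mg, 1/3 at 80 mg): the target-interval probability is 0.361 at 200 mg and 0.299 at 80 mg. Appendix 10 gives 0.372 and 0.311, and both recommend 200 mg. The differences are 0.011 and 0.012, so values within about 0.013 of the cap are not read as crossings.

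Cohort sizes are assumptions: 3 or 6 at 25 mg; 3, 6 or 9 at 80 mg; 3 or 6 at 200 mg and 400 mg. The two right-hand columns give the overdose probability at the next dose.

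| Step and data | Event not counted | Event counted |
|---|---|---|
| 80→200 mg; 25 mg 0/3; 80 mg 0/3 vs 1/3 | 0.03 | 0.28 |
| 80→200 mg; 25 mg 0/3; 80 mg 1/6 vs 2/6 | 0.16 | 0.42 |
| 80→200 mg; 25 mg 0/3; 80 mg 1/9 vs 2/9 | 0.09 | 0.27 |
| 200→400 mg; one DLT at 80 mg; 200 mg 0/3 vs 1/3 | 0.15–0.26 | 0.38–0.56 |
| 200→400 mg; none at 80 mg; 200 mg 0/3 vs 1/3 | 0.04–0.06 | 0.22–0.30 |
| 200→400 mg; none at 80 mg; 200 mg 1/6 vs 2/6 | 0.14–0.19 | 0.35–0.44 |
| 400→800 mg; no other DLT; 400 mg 0/3 vs 1/3 | 0.206–0.216 | 0.441–0.477 |
| 400→800 mg; no other DLT; 400 mg 0/6 vs 1/6 | 0.175–0.181 | 0.341–0.366 |

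In each of the last two rows the event crosses the cap in all 12 combinations of cohort sizes at the lower doses (2 × 3 × 2). At the two lower steps a clear crossing occurs only where another DLT is already counted, and not always then (1/9 vs 2/9). Adding one DLT-free participant each at 2 mg and 8 mg does not change the crossings checked: 800 mg gives 0.216 vs 0.476 with 3 per cohort, and 200 mg (1/6 vs 2/6) gives 0.148 vs 0.395.

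**The case against.** **The intended reading can be recovered.** The second bullet speaks of discontinuation, while the third speaks of DLT status and names this very event; an exception that is always overridden would be pointless. This is a fair account of intent. But the second bullet sits under a lead-in that makes everything listed a DLT. Even read as a stopping rule alone, it contradicts Section 7.3.6.

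**The window is almost empty.** Section 7.3.6 describes a Grade 3 reaction as "prolonged (eg, not rapidly responsive to symptomatic medication and/or brief interruption of infusion); recurrence of symptoms following initial improvement", or needing hospitalization, so few should clear within an hour. The one reported Grade 3 event is called hypersensitivity (Section 3.2.2.4), which has no 1-hour exception. This stands, and it limits how often the conflict will matter. The protocol nevertheless provides for the case.

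**The 1-to-6-hour part is untidy rather than harmful.** Section 7.3.2 makes discontinuation subject to 7.3.5, and a route to resume exists. That is largely right. What remains is that 7.3.5 sets restart conditions that 7.3.6 does not.

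**The 400-to-800 mg result assumes no other DLT.** Suppose the hypersensitivity event at 80 mg counts as a DLT; its cycle is not stated. Then 1/6 at 400 mg gives 0.263–0.349 at 800 mg, above 0.30 in 6 of 12 combinations and clearly so in 4. With 1/3 at 400 mg the range is 0.397–0.535, and all 12 still cross. So only the 1/6 case weakens.

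**Safeguards exist.** Grade 3 reactions reach the medical monitor within 24 hours, dose decisions are joint, and Appendix 10 has clinical assessment weigh all data. Counting the event errs toward slower escalation. All true, but for the case of up to 1 hour those reviewers hold two opposite written rules.

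**Conclusion.** The concern holds. For a Grade 3 infusion reaction back to Grade 1 within 1 hour, Section 7.3.2 B gives opposite answers on DLT status with no order of precedence. For 1 to 6 hours DLT status is settled, and only the stopping rules lack a single statement.

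The case should be rare. When it arises, one event can take the next dose across the 0.30 cap: most clearly at 400 to 800 mg, and at the lower steps mainly when another DLT is already counted. These figures rest on the Appendix 10 prior, assumed cohort sizes and a model that guides the dose decision without making it alone. The point should be fixed because the rule feeds both the escalation model and a primary endpoint component, and the repair is cheap.

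**What to change.** In the second bullet of 7.3.2 B, restrict the infusion-reaction item to reactions that do not return to Grade 1 within 1 hour, and keep the any-duration condition for the other events listed there. The 1-hour exception then governs DLT status.

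For stopping, either bring the limit in Section 7.3.6 down to 1 hour, or name the under-6-hour reaction as an explicit exception in Section 7.3.5, consistent with 8.1.1.

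Hypersensitivity would still count at any duration, so whether an event is coded as hypersensitivity or infusion reaction will matter; a sentence on how to tell them apart would help. The cost is protocol wording only, with no new data, visits or participants.
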